- To determine whether Huperzine A reduces the prevalence/frequency of post-traumatic seizures after moderate and severe TBI as compared to placebo. We hypothesize that the prevalence of seizure will be significantly lower at 12 weeks post-enrollment (immediate seizures prevalence) in subjects treated with Huperzine A relative to those treated with placebo.
- To evaluate the safety and tolerability of Huperzine A in this patient population as compared to placebo. Safety and tolerability will be assessed by a comparison of the frequency and intensity of adverse effects. We hypothesize that the incidence of clinically significant adverse effects will be no different in subjects treated with Huperzine A relative to those treated with placebo.

V. INVESTIGATORS

[name], DO Spaulding Rehabilitation Hospital

Principal Investigator

[name], PhD Spaulding Rehabilitation Hospital

Co-Investigator, recruitment, screening and consenting, data collection and analysis

[name] Spaulding Rehabilitation Hospital

Co-Investigator, recruitment, screening and consenting, cognitive assessment, outcome measurement and analysis

[name] Spaulding Rehabilitation Hospital

Research Nurse Coordinator

[name] Spaulding Rehabilitation Hospital

Co-Investigator- Study physician

[name] Spaulding Rehabilitation Hospital

Co-Investigator-Study physician

VI. SUBJECT SELECTION

We plan to enroll 30 subjects with moderate to severe TBI (Huperzine = 15, Placebo = 15).

Inclusion criteria:

- Males and females aged 18 to 65
- Meeting at least one of the following criteria for moderate or severe TBI:
 - PTA > 24 hours
 - Trauma related intracranial neuroimaging abnormalities
 - Loss of consciousness exceeding 30 minutes (unless due to sedation or intoxication)
 - GCS in the emergency department or ICU of less than 13 (unless due to intubation, sedation, or intoxication). If there is no GCS score available from the ED or ICU, the GCS from the scene can be documented.

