On a weekly basis during the 12-week active treatment period, study staff will record medication changes that have occurred since the previous week. For inpatient subjects, study staff will conduct a structured chart review and speak with the treating physician/nursing staff to identify any medication changes. For outpatient subjects, medication monitoring will be conducted through weekly phone calls. In addition to recording medication changes that have occurred over the last week, changes in baseline symptoms, side effects from Huperzine-A, adverse events and episodes of seizure activity that may have occurred in the intervening week will also be recorded. Approximately every three months after the 12-week active treatment phase (i.e., week 24, week 36, week 52), subjects will be monitored for the occurrence of any new *serious* adverse events as well as any unresolved/unstable AEs that may have occurred during the 12-week treatment period. Subjects will be instructed to call the Study Coordinator if a serious adverse event occurs between scheduled follow-ups. Serious adverse events will be reported immediately, in accordance with DSMB and IRB policies.

Drug Administration and Dosing:

Within 7 days of completion of the baseline assessment, subjects will receive the initial dose of the study drug (Huperzine A or placebo). The study drug will be prepared and stored by a third-party vendor and will be shipped to the Spaulding pharmacy. Due to changes in Massachusetts State Laws compounding pharmacies are now required to prepare and label the study drug for each individual subject. The shelf life of the study drug has been reduced from one year to six months. The study drug will be couriered to SRH hopefully, within 24 hours of receiving the prescription. Thus, the window between randomization and first dose of study drug has been increased to seven days. The randomization list will be maintained by a Spaulding pharmacist with no access to subjects or study data. Please see Appendix I for more detailed drug administration guidelines. For inpatient subjects, the study drug will be administered by nursing staff. For outpatients, instructions will be given to the subject and/or caretaker on how to continue the dosage schedule. Weekly phone calls will be made to ensure compliance.

Dose Titration:

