The starting dose of the study drug will be 100 micrograms once a day, administered in the morning. The starting dose will be continued for 4 days and will then be increased on a fixed titration schedule as follows: 100 micrograms twice a day for 4 days; 200 micrograms in the morning, 100 micrograms at night for 4 days; 200 micrograms twice a day for 4 days; 300 micrograms in the morning, 200 micrograms at night for 4 days; and then 300 micrograms twice daily for the remainder of the 12 weeks of treatment (64 days). See the table below for a summary of the study drug dosages. At the completion of the 12 weeks of dosing, all subjects will terminate study drug.

Table 2: 12-week Dosing Schedule - Titration Summary

Timeframe	Total Dose	Amount
4 Days	100 micrograms	AM: 100 Micrograms
4 Days	200 micrograms	AM: 100 Micrograms; PM: 100 Micrograms
4 Days	300 micrograms	AM: 200 Micrograms; PM: 100 Micrograms

4 Days	400 micrograms	AM: 200 Micrograms; PM: 200 Micrograms
4 Days	500 micrograms	AM: 300 Micrograms; PM: 200 Micrograms
Remainder treatment	600 micrograms	AM: 300 Micrograms; PM: 300 Micrograms
(64 days)		

Drug - Dose Intolerance:

In the case of a drug-dose intolerance, the dose of the study drug will be reduced by one dosage level. For example: from [AM: 300 mcg; PM: 300 mcg] to [AM: 300 mcg; PM: 200 mcg]. The subject will continue at the reduced dosage level for 7 days and then the dose will be escalated to the next dose level. Should the subject redevelop a drug-dose intolerance, the subject will stop the drug regimen.

Blinding Procedure:

Participants, family members, treating staff, physicians, RAs/data collectors, SRH pharmacists, site investigators and the statistician at the lead site will be blinded to group assignment until after the final analyses. The lead pharmacist who prepares the study drug kits will be blinded to group assignment. Johnson Compounding and Wellness Center, which is responsible for the randomization, will be unblinded. When Johnson Compounding and Wellness Center sends the medication to SRH for dispensing to the subject, a note indicating the contents, "Active" or "Placebo," will be with the medication. This note will be placed in a sealed envelope for storage should the subject's medication require unblinding to treat an adverse event.

Guidelines and Procedures for Breaking the Blind:

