For this aim, we will compare proportion of seizures within the first 6 weeks between Huperzine vs. placebo group using a Fisher's exact test (as we expect small numbers of expected frequencies in the cells).

• Secondary aim 3: To evaluate the safety and tolerability of Huperzine A in this patient population as compared to placebo. Safety and tolerability will be assessed by frequency of adverse effects, including laboratory abnormalities.

XI. RISKS AND DISCOMFORTS

Transcranial Magnetic Stimulation:

Note that we will be using single and paired-pulse TMS as a diagnostic tool. This type of TMS stimulation does not change cortical excitability or brain activity. There is a small chance of single pulse TMS inducing a mild, transient headache, or neck pain. TMS equipment produces a clicking sound when a current is passed through the stimulation coil. This click can result in ringing in the ear and temporary auditory threshold shifts if no protection is used. In order to prevent this potential adverse effect subjects will wear earplugs during TMS.

Electroencephalography (EEG):

The EEG test is performed to measure the electrical activity in the brain and to examine the dynamic changes. It also allows for better understanding of the effects of electrical activity generated in different areas of the brain. EEG only measures brain activity and does not induce electrical current. It is non-invasive and has been used extensively in clinical practice for diagnosis or neurological conditions such as epilepsy. There are no risks associated with EEG other than a mild discomfort caused by the tightness of the EEG net. The investigator will adjust the net to allow for the comfort of the subject.

Evetracking and pupil dilation measurement:

The eyetracking tasks that will be performed help us to measure cognitive load capabilities of the subjects. Subjects will complete both task-evoked pupillary response and smooth-pursuit eye movements by watching a high-resolution computer screen while resting their head on a headrest. There are therefore no added risks associated with this device. During the procedure, participants may experience minor discomfort resulting from sitting still and minimizing movements during the experiment. Rarely, some eye dryness or watering of the eyes may result from the test. If the subject's eyes become uncomfortable, the person administering the test will stop the procedure so the subject may rest their eyes.

Huperzine-A:

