Adverse events will be collected from the start of Huperzine A treatment through the end of study participation. During the 12 weeks of study drug, all adverse events will be collected. However, after study drug dosing is complete, we will only collect information on serious and/or unresolved/unstable adverse events that are clinically meaningful. All adverse events regardless of attribution to Huperzine A will be collected and recorded, using standard adverse event forms. All applicable local regulatory requirements related to the reporting of serious adverse events to regulatory authorities and the IRB will be followed during this study. Serious adverse events will be promptly reported to the IRB. The issue of placing the study on hold will be raised by the investigators with our local IRB if any serious adverse events occur.

Importantly, a data safety monitoring board (DSMB) will be established for the study, and will be comprised of a physiatrist (rehabilitation physician) with expertise in traumatic brain injury rehabilitation, a neuropsychologist with expertise in cognitive rehabilitation, and a biostatistician with expertise in clinical trials. This DSMB will meet after 50% of the subjects complete the study, and will meet again after 20 subjects have completed the study. The DSMB will be un-blinded in their assessment of AEs and we will adopt the following stopping rules:

- We will stop the study early if any patient dies, if any patient requires emergency surgery, or if any patient suffers a permanent and irreversible disability, only if the DSMB determines that this event was definitely or probably related to study drug.
- We will also stop the study if there is disproportionate incidence of serious adverse events in the active treatment arm vs. the placebo arm. Serious adverse effects will be defined as any adverse event, including a significant change in lab values, that is: (i) fatal, (ii) life-

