- Seizure Log: Although it is not possible within the scope of this study to obtain definitive information regarding Huperzine A's anticonvulsant properties, a detailed seizure log will be utilized to evaluate for seizure events or signs associated with seizures in Spaulding inpatients. This log will be maintained weekly by the study staff collecting data through the systematic review of the medical record and speaking to the treating medical/nursing staff. Study staff will review documented chart evidence of seizure including any EEG that is performed as part of the routine medical care. For outpatient subjects, episodes of seizure activity will be monitored through weekly phone calls.

- Suicidality Scale We will monitor for suicidality using the Columbia-Suicide Severity Rating Scale (C-SSRS) at baseline, 6 weeks and 13 weeks as requested by the FDA Division of Neurology Products per our IND.
- Adverse event monitoring: In addition to the above, we will continually monitor for changes in patient health status. The baseline symptom checklist, side effect checklist and seizure log will be used to help monitor for changes in symptoms or side effects in Spaulding inpatients, and community-dwelling outpatients. For Spaulding inpatients, we will also monitor the patient's chemistry by the scheduled laboratory exams, and monitor compliance through the medication log. By using this multimodal approach, we will be able to appropriately rate events as they occur, and to accurately associate such events to the appropriate changes in subject status (ex. whether from TBI or Huperzine, expected or unexpected, etc). In addition, approximately every three months after the 12-week active treatment phase (i.e., week 24, week 36, week 52), subjects will be monitored for the occurrence of any new *serious* adverse events as well as any unresolved/unstable AEs that may have occurred during the 12-week treatment period. Subjects will be instructed to call the Study Coordinator if a serious adverse event occurs between scheduled follow-ups. Serious adverse events will be reported immediately, in accordance with DSMB and IRB policies.

Treatment Compliance:

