Because effects will be dependent on patients taking Huperzine, treatment compliance will be essential in our study. We will measure compliance by asking the subject and/or caretaker to return the medication bottles at the end of the titration and maintenance periods. Any remaining pills will be counted, returned to the pharmacy and documented in the subject's folder, with specific forms. If the subject is still inpatient, we will monitor compliance through the medication administration system. Finally, we do not expect significant adverse effects associated with the use of Huperzine that would lead patients receiving this drug to become non-adherent.

Dropout in the placebo group:

Participants in the placebo group may disproportionately discontinue the study treatment since there will be little or no improvements in cognitive function. Although, this fact could bias the results, we expect that the placebo group will also have a small improvement (due to natural recovery, though smaller than in the active group) and we will conduct an analysis of the data using an intent-to treat population, to protect against disproportionate dropout.

XIII. POTENTIAL BENEFITS

It is possible that subjects participating in this research may benefit from the Huperzine-A given in the trial. Additionally, subjects may benefit from the use of TMS as the data could suggest plasticity changes and encourage clinicians to continue therapy or other interventions. Lastly

subjects may benefit from the close follow-up and enhanced observation of the clinical research team.

XIV. STIPEND

Each subject will receive a total of \$450 paid throughout their study participation. The stipend payment distribution is as follows: Screening \$25, Baseline \$25, Week 6 \$50, Week 12 \$100, Week 13 \$50, Week 24 \$100 and Week 52 \$100.

In addition, travel, parking and/or hotel costs will be reimbursed up to \$200/ subject. Proof of payment of costs will be required for reimbursement.

Plan for Future Studies:

A major goal of this study is to collect data that may be useful to plan future phase II/III trials. In fact, this is one of the major goals of phase II studies that usually test several outcomes as there are no strong data to support a large trial. Therefore, with this study we expect to:

- (1) Determine parameters for sample size calculation such as effect sizes for different endpoints.

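### Secondary aim 2 hypothesises fewer seizures at 12 weeks, but its only stated test counts the first 6 weeks

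*Combined protocol and SAP*

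**What the plan says.** Section IV (Specific Aims, Secondary Aims) words the seizure aim without a time point. Its hypothesis has one: "the prevalence of seizure will be significantly lower at 12 weeks post-enrollment (immediate seizures prevalence").

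Section X (Statistical Analysis, Secondary aim 2) repeats the aim, again without a time point, and gives one analysis: "we will compare proportion of seizures within the first 6 weeks between Huperzine vs. placebo group", by Fisher's exact test. The start of the 6 weeks is not defined.

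The data run further than that test. Section VIII (Study Visit Summary) describes weekly contact through the 12-week treatment period, at which "episodes of seizure activity that may have occurred in the intervening week will also be recorded". Table 1 and the Seizure Log paragraph in Section XII also describe weekly seizure monitoring.

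Three other places bear on the point:

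- Section XI states "During the 12 weeks of study drug, all adverse events will be collected", and Section X allows Fisher's test for proportions of adverse effects.
- The Seizure Log paragraph concedes that "it is not possible within the scope of this study to obtain definitive information regarding Huperzine" A's anticonvulsant properties.
- The Plan for Future Studies lists as an output: "Determine parameters for sample size calculation such as effect sizes for different endpoints".

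**The concern.** A hypothesis about 12 weeks and a test of the first 6 weeks concern different quantities. The plan neither explains the change nor supplies a 12-week seizure comparison for this aim. The primary aim shows that the windows can agree: its hypothesis is at 12 weeks and its test uses Week 12 minus baseline.

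Two things are at stake. First, the seizure effect estimate carried forward to plan later trials would describe only the first half of treatment, which includes the whole titration period, while the hypothesis refers to 12 weeks. Second, with two windows in one document and neither named as the governing one, the choice could be made after the results are known.

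The analysis sentence has a related looseness. It speaks of a proportion of seizures, whereas Fisher's test here needs a proportion of subjects, that is, those with at least one seizure.

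**Working it through.** **What there is to reproduce.** The plan gives no seizure risk, event count, sample size or power for aim 2. Its only sample-size derivation (26 subjects, 13 per group) is for the CVLT-II and plays no part here. The dosing calendar does reproduce: five titration steps of 4 days make 20 days, and 84 − 20 = 64, the figure in Section VIII, Dose Titration ("300 micrograms twice daily for the remainder of the 12 weeks of treatment (64 days")).

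**The two windows, counted from first dose.**

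- Hypothesis: 12 × 7 = 84 days. Test: 6 × 7 = 42 days. Omitted: 42 of 84 = 50%.
- Final-dose days within the first 42: 42 − 20 = 22. Omitted: 64 − 22 = 42 of 64 = 66%.
- Scheduled amount: 4 × (100 + 200 + 300 + 400 + 500) = 6,000 micrograms in titration, plus 64 × 600 = 38,400, total 44,400. By day 42: 6,000 + 22 × 600 = 19,200. Omitted: 25,200 of 44,400 = 57%.

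These are scheduled figures and ignore dose reductions for intolerance.

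**Effect of the clock start.** Section VIII says "the window between randomization and first dose of study drug has been increased to seven days". It also allows 7 days from randomization to complete baseline and 7 more to first dose, which together could reach 14. If first dose falls L days after the clock starts, the 6-week window holds 42 − L dosing days and the 12-week window 84 − L. The difference is 42 days at L = 0, 7 or 14, and all 42 come after dosing day 20. The lag is thus a separate question and does not change the size of the mismatch.

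**Illustration of the effect on the estimate.** All risks here are assumptions. Let p be the 12-week placebo risk, with a constant hazard, a hazard ratio of 0.5 and 15 subjects per arm.

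- 6-week placebo risk: q = 1 − (1 − p)^0.5
- Active risk: 1 − (1 − p)^0.5 at 12 weeks and 1 − (1 − q)^0.5 at 6 weeks
- Power: exact enumeration of the two-sided Fisher test at 0.05

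| p | Expected placebo subjects with a seizure, 12 wk / 6 wk | Risk difference in points, 12 wk / 6 wk | Power, 12 wk / 6 wk |
|---|---|---|---|
| 5% | 0.75 / 0.38 | 2.5 / 1.3 | 0.04% / 0.002% |
| 20% | 3.0 / 1.6 | 9.4 / 5.1 | 3.8% / 0.7% |
| 40% | 6.0 / 3.4 | 17.5 / 10.6 | 8.3% / 4.6% |

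Halving the 12-week risk instead of the hazard gives powers of 0.04–11.2% and below 0.01–5.6% over the same range, and the reading is the same. With no seizures on active drug, 4 placebo subjects with a seizure give p = 0.0996 and 5 give p = 0.042, so at least 5 of 15 are needed for significance.

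**The case against.** The strongest reply is that little follows from the mismatch. This is a secondary aim of an exploratory study that itself disclaims definitive seizure information, and the power figures show that no plausible test decision would change. That stands, and it limits the weight of the point.

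Later seizures are also not lost. All adverse events are collected for 12 weeks, and Section XI names a seizure without hospital admission as an event that would typically count as serious, so it would normally enter the data safety monitoring board's comparison of serious events by arm. This stands too, but that comparison serves safety review and stopping. It is not the aim 2 analysis.

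The illustration has a limit. Under a constant hazard ratio the relative effect is identical in both windows, and the larger 12-week risk difference comes simply from longer follow-up. It does not show that a 6-week relative effect would be biased. The shares of full-dose days and micrograms matter only if any seizure effect depends on dose or time, and the documents give no human data on that. What remains is that the plan compares proportions, and a difference in proportions depends on the window.

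Finally, prevalence at 12 weeks could mean either the cumulative proportion through Week 12 or the proportion with seizures around Week 12. The 42-day figure rests on the cumulative reading. On the other reading the 6-week test does not reach the hypothesised time point at all, so the mismatch remains either way.

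**Conclusion.** The concern holds. The only test stated for secondary aim 2 does not address the hypothesis stated for it, and nothing in the documents reconciles the two. On the cumulative reading the test omits 42 days, half of the treatment period, all of them scheduled at the final dose level. This follows from the documents' own calendar and needs no assumption about seizure risk. The illustrative risk differences and powers rest on an assumed 12-week placebo risk of 5–40%, a constant hazard and a hazard ratio of 0.5, and the conclusion does not depend on them.

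The consequence is moderate. The primary outcome, the sample size and the safety rules are unaffected, and aligning the windows would not make the seizure comparison well powered. It would make the reported estimate the one hypothesised. This should be corrected. The documents do not show which window was intended.

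**What to change.** Before unblinding, reconcile the hypothesis in Section IV with the analysis in Section X:

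- **Endpoint:** the proportion of subjects with at least one seizure through Week 12. This follows the stated hypothesis and the treatment period, and replaces the reference to a proportion of seizures.
- **Clock start:** one start, used in both sections. First dose is the practical choice. Weekly recording is tied to the treatment period and adverse-event collection begins with treatment, so a clock started at enrollment could include days without seizure records.
- **Analysis:** Fisher's exact test between arms, with the 6-week proportion reported as supportive.

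If 6 weeks was the intended window, change the hypothesis in Section IV to match and give the reason.

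The cost is wording in two sections. With the first-dose clock, the weekly seizure records already cover the period, so no added visits, data collection or subjects are needed.

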The anticipated loss to follow-up rate in this study is around 15% - like our other drug studies. To account for this loss-to-follow-up rate, a total of 15 patients per group (30 total) will be enrolled in the study. The primary analysis will be an intent-to-treat analysis that will include all randomized participants regardless of their compliance with the study treatment or follow-up schedule. Study subjects should have received at least 1 dose of study drug/placebo. All hypothesis testing will be conducted using $\alpha = 0.05$, two-sided.

To analyze the data, we will compare means using t-test and modeling the data with ANOVA for multivariate analysis controlling for baseline values and other important covariates. If necessary, non-parametric approaches including Mann-Whitney and Friedman's test for multivariate analysis will be used with data that are not normally distributed. We will also use Fisher's exact test for comparison of categorical variables such as proportion of adverse effects. In summary, we will use the following statistical tests according to our primary aims:

• Primary Aim: To determine whether Huperzine A, as compared with placebo, has a differential effect on learning and memory functions after moderate to severe TBI.

For this aim we will compare means using t-test (comparing differences (Week 12 – baseline) between the two groups) and modeling the data with ANOVA for multivariate analysis controlling for baseline values and other important covariates (for secondary analysis). If necessary, non-parametric approaches including Mann-Whitney and Friedman's test for multivariate analysis will be used with data that are not normally distributed.

• Secondary aim 1: To determine whether administration of Huperzine A produces significant differences in neurophysiologic markers (as indexed by EEG event related potentials (P50 and P300) and TMS-indexed cortical excitability (cholinergic activity)) associated with cognition, relative to a placebo.

For this aim we will also build models in which the main dependent outcome will be amplitude or latency measures (from P50, P300 and SAI) and the independent variables will be group, time and the interaction group*time.

• Secondary aim 2: To determine whether Huperzine A reduces the prevalence of post-traumatic seizures after moderate and severe TBI as compared to placebo

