- Study Drug Blood Levels: Blood samples will be drawn from 10% of subjects to assess efficacy vs. steady- state HupA concentrations and tolerability during the maintenance phase. Samples will be drawn pre-dose and 1 hour post dose on Day 21 or Day <21 (at the end of dose escalation for each patient in the 10%, whatever dose they escalate to). During the maintenance phase a weekly pre-dose sample will be drawn. Week 12, on the last day of dosing, a pre-dose and 1 hour post-dose sample will be drawn. These samples will be processed in the SRH clinical labs, stored at -80, and then forwarded to the Illinois Institute of Technology Research Institute (IITRI) in Chicago. De-identified samples will be shipped to IITRI and the link to the code will remain at SRH and not be provided to IITRI.
- Baseline Symptom Checklist: This will be completed before study drug is started. After treatment is initiated, the study staff should use the baseline symptom checklist list as a reference to identify and code new symptoms that arise after treatment is initiated, or to detect an exacerbation of a previously-noted symptom. For Spaulding inpatients, these data will be collected from systematic medical record review and also from speaking with the treating medical/nursing staff on a weekly basis. For outpatient, changes in baseline symptoms will be monitored through weekly phone calls.
- Drug Side Effects Checklist: For Spaulding inpatients, the study staff will evaluate potential side effects of Huperzine A using the drug side effect checklist during weekly systematic review of the medical record. This scale covers all known possible side effects of Huperzine A. In addition to speaking with medical/nursing staff, the subjects/caregivers may be asked to report whether they have experienced any side effects in an open-ended manner, and any side effects experienced by patients will be marked on a scale of 1 through 3 to measure severity (1- Mild, 2- Moderate, 3- Severe). If any side effects are reported, the degree of relatedness to the Huperzine A intervention will be assessed. For outpatient, side effects from Huperzine-A will be monitored through weekly phone calls.

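### Secondary Aim 3 promises to compare the frequency and intensity of adverse effects, but its analysis text covers frequency only, so severity grades are never compared by arm

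*Combined protocol and SAP*

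**What the plan says.** All references are to the combined protocol and SAP.

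- **Section IV, Specific Aims (third secondary aim):** "Safety and tolerability will be assessed by a comparison of the frequency and intensity of adverse effects". The accompanying hypothesis is that "the incidence of clinically significant adverse effects will be no different in subjects treated with Huperzine A relative to those treated with placebo". The protocol does not define clinical significance and gives no margin for being no different.
- **Section X, Statistical Analysis, Secondary aim 3:** "Safety and tolerability will be assessed by frequency of adverse effects, including laboratory abnormalities". Intensity is absent, and no test is named under the aim.
- **Section X, general analysis paragraph:** "We will also use Fisher's exact test for comparison of categorical variables such as proportion of adverse effects". This is the only test tied to adverse effects.
- **Section XII, Drug Side Effects Checklist:** "any side effects experienced by patients will be marked on a scale of 1 through 3 to measure severity", with 1 mild, 2 moderate and 3 severe. This sits in text about Spaulding inpatients. For outpatients the entry mentions only monitoring by weekly telephone call.
- **Section VIII, Drug - Dose Intolerance:** "In the case of a drug-dose intolerance, the dose of the study drug will be reduced by one dosage level", and later "Should the subject redevelop a drug-dose intolerance, the subject will stop the drug regimen". These are defined events, but no section makes them an outcome.

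Section X also names tolerability as one of the things the study is designed to address.

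**The concern.** The aim and its analysis do not match. Both are current text, so neither supersedes the other. Anyone who follows Section X as written will report how often adverse effects occurred and will not report how bad they were in each arm, although Section IV commits to both.

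This matters for two reasons. First, Section XI lists many symptoms expected from the brain injury itself, and all adverse events during dosing are recorded whatever their cause. A high event frequency in both arms is therefore plausible, and severity could be where a drug effect shows. Second, the hypothesis is one of no difference, so a summary that cannot register intensity leans towards the result the aim expects. The trial is meant to inform a later phase II/III study, which will need severity by arm.

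**Working it through.** **Step 1. Is intensity restored anywhere else?**

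| Place | Frequency by arm | Intensity by arm |
|---|---|---|
| Section IV, Aim 3 | yes | yes |
| Section X, Aim 3 analysis | yes | no |
| Section X, Fisher sentence | yes (proportions) | possible, not committed |
| Section XI, DSMB stopping rules | serious events only | no (seriousness, not grade) |
| Section XII, checklist | collection only | collection only |

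No section commits to a by-arm comparison of grade. The plan gives no power, sample size or event rate for Aim 3, so there is no planned figure to reproduce. The 26 subjects (13 per group) in Section X concern the CVLT-II.

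**Step 2. Can frequency agree while grades differ?** The input from the plan is 15 per arm (Section X). The counts are assumed.

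| Worst grade | 0 | 1 | 2 | 3 |
|---|---|---|---|---|
| Placebo | 3 | 12 | 0 | 0 |
| Active | 3 | 4 | 4 | 4 |

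- Any event: 12/15 against 12/15, Fisher p = 1.00.
- Worst grade, Mann-Whitney U for active, counting each active-placebo pair as 1 if active is worse and 0.5 if tied:
  - 3 active at grade 0: 3 × (0.5 × 3) = 4.5
  - 4 active at grade 1: 4 × (3 + 0.5 × 12) = 36
  - 8 active at grade 2 or 3: 8 × 15 = 120
  - U = 160.5. The probability that an active subject is worse, counting ties as half, is 160.5 / (15 × 15) = 0.71; p = 0.031.
- Moderate or severe: 8/15 against 0/15. Fisher p = 2 × C(15,8) / C(30,8) = 2 × 6,435 / 5,852,925 = 0.002.

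A less extreme assumed split (placebo 3/10/2/0, active 3/3/5/4) gives Fisher p = 1.00 on any event and Mann-Whitney p = 0.046.

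**Step 3. Illustrative rejection rates at 15 per arm, two-sided 0.05.** Fisher power is the exact sum, over all pairs of counts (a, b) that Fisher rejects, of Bin(a; 15, p1) × Bin(b; 15, p0). The rank test on worst grade (0-3) is simulated. All rates are assumed.

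| Scenario (placebo vs active) | Fisher, any event | Fisher, moderate or severe | Rank test |
|---|---|---|---|
| Any 80% vs 80%; moderate/severe 20% vs 55% | 1.7% | 33.9% | about 30% |
| Any 80% vs 90%; moderate/severe 25% vs 60% | 4.1% | 33% | about 49% |

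Grade probabilities for none/mild/moderate/severe in the first row are 20/60/15/5% vs 20/25/35/20%; in the second, 20/55/20/5% vs 10/30/35/25%.

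The gain comes from bringing severity into the endpoint. In the first row Fisher's test on a severity threshold does as well as the rank test.

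**Step 4. Intolerance stops.** With assumed counts, 5/15 vs 0/15 gives Fisher p = 0.042 and 4/15 vs 0/15 gives p = 0.0996. The exact 95% interval for 4/15 is about 8% to 55%. These outcomes suit estimation better than testing.

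**The case against.** The strongest reply is that Section X leaves room. Its Fisher sentence gives the proportion of adverse effects only as an example of a categorical variable, so a test by severity category would be allowed. The hypothesis in Section IV also speaks of clinically significant effects, which hints at a threshold. Both points are fair, and they show that Fisher's test is not itself at fault. But permission is not commitment: the threshold is undefined and does not reappear in the Aim 3 analysis.

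A second reply is that the trial is exploratory and has an unblinded DSMB with a serious-event rule. That protects subjects, but seriousness is not intensity. Non-serious effects that lead to a dose reduction would not trigger the rule.

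A reader might also infer more than the documents support:

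- **That the plan will test a single any-or-none endpoint and so has almost no chance of seeing a severity difference.** No section specifies that endpoint. The low figures in the first Fisher column depend on assuming it, and on rates the documents do not give.
- **That intolerance stops contradict the aim by being left out.** Aim 3 never promises them. They are an omission against the word tolerability.
- **That stopping for intolerance hides events by shortening exposure.** A subject who stops for intolerance has normally already had an event, so an any-event proportion barely changes. An effect on total counts would depend on stopping rates and timing that are not in the documents.
- **That a severity analysis would settle tolerability.** At 15 per arm it would still miss the illustrated differences in half or more of trials.

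**Conclusion.** The point holds as a mismatch between the aim and its analysis. Section IV commits to frequency and intensity, Section X analyses frequency, and nothing elsewhere supplies the by-arm severity comparison. A frequency-only result can therefore read as no difference while grades differ.

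That conclusion rests on the text alone. The size of the loss cannot be derived from the documents, so the p-values and rejection rates above are illustrations under assumed event rates. The documents do not support a claim that the drug is poorly tolerated or that the plan would conceal it. The change should be made, but it does not threaten the primary analysis.

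**What to change.** 1. Amend the Secondary aim 3 text in Section X to compare each subject's worst severity grade during dosing (0 = none, 1-3) by arm. This could use Mann-Whitney or the proportion with a moderate or severe event; choose one in advance. Report an effect estimate with a confidence interval. Keep the frequency comparison. Because no margin is defined, do not read a non-significant result as evidence of no difference.
2. State in Section XII that the 1-3 grade is recorded for outpatients in the weekly calls as well as for inpatients. The current text does not say so, and a worst-grade analysis depends on it.
3. As a descriptive addition, report by arm the number of subjects with a dose reduction, with a stop for intolerance, and completing at the target dose, each with an exact interval.

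The cost is a short SAP amendment, a few tables and a small clarification of outpatient data capture. The downside is a few more descriptive comparisons in a small exploratory trial. No dose, visit or clinical rule changes.
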